4.3.4 Assignment of AEs to Treatment Period

Each AE will be assigned to a treatment period using date of vaccination (or infusion if this is the final treatment) and date of onset of AE:

- All AEs beginning before the first treatment with trial product will be classified as pre-treatment AEs belonging to the Screening Phase.
- All AEs starting on the day of first MVA-BN-CV301 vaccination until the day prior to the first FPV-CV301, or until early treatment termination, will be assigned to the MVA Vaccination Period.

- All AEs starting after the first FPV-CV301 vaccination through 30 days post-last trial product, or until early termination, will be assigned the FPV Vaccination Period.
- All AEs starting after the first dose of trial product through 30 days post last trial product (CV301 or atezolizumab, whichever is latest) will be included in the Overall Treatment Period.
- Related SAEs and AESIs starting after 30 days but prior to 100 days after the last trial product dose will be assigned to the FU phase of the trial. Other AEs (i.e., not serious or unrelated) occurring during the same time period will be assigned to the FU phase but excluded from tables, if collected, as they are not considered treatment emergent.

If an AE coincides with the date of a vaccination, the AE will be assigned to the treatment period corresponding to the vaccination on this date to be conservative.

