Trial medication refers to dosing with atezolizumab.

Treated Subjects

A subject is considered treated once they have received the first dose of trial product.

Trial Day (Study Day)

The day of trial is defined from the day of first vaccination. The day of first vaccination is defined as Day 1, the day after first vaccination is Day 2, and so on. Similarly, the day before first vaccination in the screening period is defined as Day -1, and so on. Note, no reference is made to the time of the vaccination in the calculation of the trial day, i.e., at midnight a new trial day begins regardless of the time of first vaccination. Note, to maintain conformance with Clinical Data Interchange Standards Consortium (CDISC) data standards, in datasets “trial day” will be referred to as “study day.”

Baseline

If not otherwise specified, “baseline” refers to the last measurement prior to first treatment with vaccine, including re-screening or pre-treatment unscheduled visit values. Note for determination of baseline values, data that are collected on the day of first vaccination but prior to the first vaccination, per protocol, will be considered pre-treatment data and will be eligible to be used as baseline values. Baseline data will be summarized without specification as to which visit the data were originally reported.

In cases where no pre-treatment values exist for a baseline parameter within a subject, the subject will be considered as having no baseline, and post-baseline changes and percent changes will not be able to be calculated.

Screening Phase

All data collected from the initial screening visit (within 28 days prior to first dose) until first dose of trial vaccine. This may include any unscheduled or re-screening visit results up to the first trial vaccination.

Active Trial Phase

All data collected at the visit of first vaccination (Visit 1) through Visit 14 plus 30 days, including unscheduled visits, will be considered part of the active trial phase. For safety analyses, data will be collected until 30 days (Visit 14 for completers) after the last treatment. For subjects who discontinue treatment early, the 30 days will start at the most recently received trial product.

Long Term Follow-up (LTFU) Period

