A TEAE is an AE with an onset on or after initiation of trial product, or an AE present at initiation of trial product that worsens. This includes all AEs occurring from first dose of trial product through 30 days after of last dose of trial product, if unrelated to trial product or non-serious. All trial product-related SAEs and AESIs through 100 days after the last dose of trial product will be counted as TEAEs.

Related TEAEs

A TEAE is determined to be related to trial product for the purpose of CSR reporting if assessed by the investigator as possible, probable, or definitely related to trial product. If a relationship is missing and the TEAE started after the initiation of an individual trial product, then the TEAE will be analyzed as being related to that individual trial product. Relationship will be collected separately for MVA-BN-CV301, FPV-CV301, and atezolizumab.

Serious Adverse Events

AEs that meet the seriousness criteria as described in Section 8.1.4 of the trial protocol are considered serious adverse events (SAEs). Collection of SAEs begins at the signing of the ICF and continues for 30 days after the last treatment with trial product for unrelated events, and for 100 days after the last dose for treatment-related events.

Severe Adverse Events

AEs are graded for severity using the National Cancer Institute's Common Terminology Criteria for Adverse Events (NCI CTCAE) version 5.0. Levels include 1: Mild, 2: Moderate, 3: Severe, 4: Life Threatening, and 5: Death. For analysis, severe AEs will include AEs \geq Grade 3.

Adverse Events of Special Interest

AEs of special interest (AESIs) include Immune-mediated AEs (IMAEs) and cardiac events but may also include other events based on the opinion of the investigator. Autoimmune diseases and immune-mediated clinical syndromes, occurring after first treatment with trial

product, will be reported as potential IMAEs. In addition, cardiac events are considered AESIs. A Cardiac AESI is defined as:

- Any cardiac sign or symptom (attributed by the investigator to be cardiac related) developed since the first vaccination
- ECG abnormalities determined to be clinically significant developed since the first vaccination

Additionally, for atezolizumab AESIs will be reported based on the manufacturer's requirements (See trial protocol section 8.1.3 for further details).

1 Introduction

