4.4.8 Safety Variables and Analyses

4.4.8.1 Adverse Events

Variables

- **Baseline Signs and Symptoms (pre-treatment AEs)**
Any AE recorded between ICF signing and first treatment with trial product, regardless of seriousness.
- **TEAEs**
- **SAEs**
- **AESIs**
AESIs include IMAEs and Cardiac events. IMAEs will be collected from the “Potential IMAE” CRF page where the question “Does this event have an immune-mediated etiology or an immune-mediated component?” on the IMAE page is marked as “Yes.” Cardiac AESIs will be identified where “AESI?” is marked as Yes on the AE CRF page. As events coded as “Cardiac disorders” per MedDRA SOC and ECGs with clinically significant abnormalities are considered AESIs, cross checking will be performed to ensure all clinically significant ECG results have a corresponding AE in the database prior to database lock. In addition, Troponin I laboratory testing will also be cross checked versus the AE page in the CRF if results are deemed clinically significant by the investigator.
- **Relationship to trial product (MVA-BN-CV301, FPV-CV301, atezolizumab)**
Relationship is collected as unrelated, unlikely, possibly, probably, or definitely related on the AE CRF page. AEs reported as possibly, probably, or definitely related, along with any missing relationship values, will be summarized as related to the treatment of interest. For overall trial product relationship summaries, if any of the three individual trial products are considered related to the AE, the overall relationship will be defined as related to trial product.
- **Severity of AEs (per CTCAE v5.0 grade)**
TEAEs will be categorized as 1: Mild, 2: Moderate, 3: Severe, 4: Life Threatening, or 5: Death on the AE CRF page. For summaries, severe AE displays will include all AEs \geq Grade 3
- **TEAEs leading to Treatment Discontinuation**
Treatment discontinuation will be identified as an AE with an action taken of “Drug Withdrawn” for any of the three trial products.
- **TEAEs leading to Death**

TEAEs with either an outcome of “Fatal” or a severity of “5: Death” will be considered TEAEs leading to death.

Analyses

Summary tables will be presented by treatment period (MVA Vaccination Period, FPV Vaccination Period, and Overall Treatment Period), cohort, and overall including frequency and incidence of AEs, and ordered by descending incidence of SOCs and PTs for the following categories:

- Any TEAEs
- Non-Serious TEAEs occurring in $\geq 5\%$ of either cohort or overall

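### SAP 4.3.4 does not map every treatment-emergent adverse event to a tabulated period: worsened pre-dose events and related SAEs/AESIs after day 30 have no period table, and the MVA and FPV sub-tables cut the 30-day tail

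*SAP*

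**What the plan says.** **Definition.** The SAP's General Definitions give the TEAE three limbs beyond plain new onset on treatment:

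- Worsening: "or an AE present at initiation of trial product that worsens". Protocol 9.9.1 has the same limb and explains worsening as an on-study grade above the baseline grade or a reported relationship to trial product.
- A 30-day tail: "This includes all AEs occurring from first dose of trial product through 30 days after of last dose of trial product", for events that are unrelated or non-serious. Under Active Trial Phase the SAP adds: "For subjects who discontinue treatment early, the 30 days will start at the most recently received trial product".
- A 100-day tail: "All trial product-related SAEs and AESIs through 100 days after the last dose of trial product will be counted as TEAEs". Protocol 9.9.1 requires these events to be summarized by system organ class (SOC), preferred term (PT) and grade.

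**Period rules.** SAP 4.3.4 assigns each event from its onset date and the dosing dates:

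- Screening Phase: "All AEs beginning before the first treatment with trial product will be classified as pre-treatment AEs belonging to the Screening Phase".
- MVA period: from the first MVA-BN-CV301 dose to the day before the first FPV-CV301 dose, or to early treatment termination.
- FPV period: from the first FPV-CV301 dose "through 30 days post-last trial product, or until early termination, will be assigned the FPV Vaccination Period".
- Overall period: events starting after the first dose, to 30 days after the last trial product, with no early-termination clause.
- Follow-up phase: related SAEs and AESIs that start after day 30 and before day 100. Other late events also go here but are kept out of tables.

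**Displays.** SAP 4.4.8.1 states: "Summary tables will be presented by treatment period (MVA Vaccination Period, FPV Vaccination Period, and Overall Treatment Period", with cohort and overall columns. For SAEs and AESIs after the treatment period it names a listing. A separate TEAE overview table by category is not tied to a period.

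**The concern.** A definition says which events count; a period rule says in which table each one appears. If the second does not follow from the first, an event can meet the definition and still have no table.

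Safety of the combination is a secondary endpoint, measured by the incidence, severity and seriousness of TEAEs. Two of the limbs at issue carry particular weight. Worsening of an existing complaint is a usual way for toxicity to show itself in patients with advanced cancer. The 100-day window exists, by protocol 8.3.1, because a delayed immune effect of the checkpoint inhibitor is possible. SAP 4.5 declares no departure from the protocol's analyses, so an omission here would not be visible as a change. Two programmers working from the same text, one from the definition and one from the period rules, could produce different TEAE tables.

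**Working it through.** The plan gives no figure to reproduce, so the check sets the definition against the period rules.

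**Inputs.** First dose is Day 1 (SAP, Trial Day). A new-onset event is a TEAE if (onset − last dose) ≤ 30, or if it is a related SAE or AESI and (onset − last dose) ≤ 100. A pre-dose event is a TEAE if it worsens. Periods follow 4.3.4 as summarized above. The event and stopping dates below are assumed for illustration. The FPV early-termination clause is read as the end of treatment.

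| Illustrative event | Days after last dose | TEAE? | Period under 4.3.4 |
|---|---|---|---|
| Onset Day −5, worsens Day 10 | not applicable | Yes | Screening only |
| MVA dose Day 1 only, treatment ended Day 5, onset Day 20 | 20 − 1 = 19 | Yes | Overall, not MVA |
| Last dose FPV Day 43, treatment ended Day 50, onset Day 60 | 60 − 43 = 17 | Yes | Overall, not FPV |
| Completer, last dose Day 694, onset Day 714 | 714 − 694 = 20 | Yes | FPV and Overall |
| Completer, related SAE or related AESI, onset Day 754 | 754 − 694 = 60 | Yes | Follow-up only |
| Completer, related SAE, onset Day 794 | 794 − 694 = 100 | Yes | None |
| Completer, related but non-serious and not an AESI, or unrelated SAE, onset Day 754 | 60 | No | Follow-up, out of tables |

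**Worsened events (row 1).** Period assignment never uses the worsening date, and the Overall period admits only events that start after the first dose. SAP 4.4.7.6 summarizes pre-dose events separately, as baseline signs and symptoms. The event would be tabulated by period only if the worsening were entered as a new event with its own onset. Protocol 8.2.3 asks for that for clinically significant examination findings; neither document states it for adverse events already open at first dose. Such events will exist, because collection starts at consent.

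**Related SAEs and AESIs, days 31 to 100 (rows 5 and 6).** The Overall period ends at day 30 and the follow-up phase is not among the three tabulated periods. At exactly day 100 the two texts disagree: the definition includes that day and 4.3.4 stops short of it.

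**Thirty-day tail (rows 2 and 3).** The MVA rule has no tail for a subject who stops before FPV-CV301. The FPV rule has one but adds an early-termination clause. Both conflict with the Active Trial Phase text, which runs the 30 days from the last product received. The FPV clause is also ambiguous, since the SAP defines early treatment discontinuation and early trial discontinuation separately. The Overall period keeps these events.

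**Size.** Section 4.4.8.1 computes incidence as subjects with the event over subjects in the cohort. If a misplaced event is a subject's only event in its category, the shift is 1/n:

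- Stage 1 only: 1/14 = 7.1% (Cohort 1), 1/13 = 7.7% (Cohort 2), 1/27 = 3.7% (overall).
- Full enrollment: 1/33 = 3.0%, 1/35 = 2.9%, 1/68 = 1.5%.

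**The case against.** The best defence is that the intent is plain. The definition says outright that related SAEs and AESIs to day 100 count. Sections 4.3.4 and 4.4.8.1 expressly keep only the other late events out of tables, which implies that these stay in. The overview table is not tied to a period and could hold them. A worsening may well be entered as a new line under the eCRF Completion Guidelines, a separate document not available here, and every adverse event is listed in any case. These are descriptive summaries in a single-arm Phase 2 trial.

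Much of that stands, and it limits the point. It does not close the gap: an implied intent to tabulate is not a table, the overview gives counts by category rather than by SOC and PT, and the Screening Phase rule for pre-dose onset is explicit and has no exception.

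Several stronger readings are tempting and are not supported:

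- That early stoppers' events vanish from the TEAE tables. They do not; the Overall period keeps the full 30 days.
- That the days cut from the MVA or FPV period measure how far rates are understated. This would need termination to be dated at the last dose, which no text says, and incidence here is per subject, not per day at risk.
- That MVA and FPV incidences should add up to Overall. A subject can count in both periods.
- That serious or fatal events cluster in early stoppers. Nothing in the documents says so.
- That all related events after day 30 are misplaced. Related events that are neither serious nor AESIs are not TEAEs after day 30, so their exclusion is consistent.

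**Conclusion.** The point holds in three parts of unequal weight.

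1. **Worsened events** are the firmest part: a stated rule contradicts the definition. How many events are affected depends on whether sites enter a worsening as a new event, so it would be wrong to say that every such event is lost.
2. **Related SAEs and AESIs after day 30** lack an assigned SOC and PT table that the protocol requires, and day 100 itself falls in no period. This is a gap in placement; the text does not exclude these events from tables.
3. **The cut 30-day tail** can understate the MVA and FPV sub-tables only. For FPV this assumes that the early-termination clause means the end of treatment.

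The documents do not allow the number of affected events to be estimated. The per-subject shifts of 1.5 to 7.7 percentage points show only what one such event can do. The efficacy analyses are not touched. The text should be corrected before the safety tables are programmed.

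**What to change.** - Assign an adverse event that worsens after the first dose by its worsening date. If the eCRF holds no such date, instruct sites to record the worsening as a new adverse event line.
- End the MVA period at the earlier of the day before the first FPV-CV301 dose and 30 days after the last trial product.
- Delete the early-termination clause from the FPV rule, leaving 30 days after the last trial product as its end.
- State that the Overall TEAE tables, including those by SOC, PT and grade, also count related SAEs and AESIs through day 100 inclusive, and align the follow-up bullet in 4.3.4 with that boundary.

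The cost is SAP wording and the matching derivation. No new data are needed if worsening dates are already captured; otherwise, one eCRF instruction.

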## 1.4 Protocol Synopsis

Title	A Phase 2, Multicenter, Single-Arm Trial of CV301 in Combination with PD-1/L1 Blockade in Patients with Locally Advanced or Metastatic Urothelial Bladder Cancer
Clinical phase	Phase 2
Sponsor	Bavarian Nordic A/S 
Number of sites	Approximately 12
Vaccination dose, schedule and administration route	
Prime with MVA-BN-CV301 (nominal titer <math>1.6 \times 10^9</math> Inf.U) given subcutaneously (SC) on Day 1 and Day 22. One dose = four 0.5 mL injections. One injection = nominal titer <math>4 \times 10^8</math> Inf.U in 0.5 mL.
 
Boost with FPV-CV301 (nominal titer of <math>1 \times 10^9</math> Inf.U in 0.5 mL, given SC every 21 days for 4 doses (on days 43, 64, 85, and 106), followed by boosts every 6 weeks until 6 months on trial (i.e., days 148 and 190), then every 12 weeks until completion of 2 years. One dose = one 0.5 mL injection.
 
Atezolizumab fixed dose of 1200 mg intravenous on Day 1 of each 21-day cycle. No dose reduction permitted.

Trial duration	Approximately 104 weeks before starting the long term follow up.
Trial Population	
Patients with Locally Advanced or Metastatic Urothelial Cancer (UC) including bladder, ureter, renal pelvis and urethra.
 
Cohort 1: Ineligible for cisplatin-containing chemotherapy (first-line treatment)
 
Cohort 2: Previously treated with standard first-line cisplatin-based chemotherapy, PD-1/L1 Naïve (second-line treatment)

Number of Subjects:	Approximately up to 68
Primary objectives	Objective Response Rate (ORR; Complete Response [CR] + Partial Response [PR] Rate) as per Response Evaluation Criteria in Solid Tumors version 1.1 (RECIST 1.1)

Secondary objectives	Progression-Free Survival (PFS)  Overall Survival (OS)  Duration of Response  Safety of the treatment combination of CV301 with atezolizumab

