4.4.8 Safety Variables and Analyses34

4.4.8.1 Adverse Events34

4.4.8.2 Clinical Laboratory Assessments37

4.4.8.3 Vital Signs and ECG38

4.4.8.4 Physical examination39

4.5 Alterations to the Clinical Trial Protocol39

5 References40

Abbreviations

Abbreviation	Definition
AE	Adverse Event
AESI	Adverse Event of Special Interest
ADR	Adverse Drug Reaction
ALT	Alanine Aminotransferase
AST	Aspartate Aminotransferase
ATC	Anatomic-Therapeutic-Chemical
β-HCG	Beta-Human Chorionic Gonadotropin
BMI	Body Mass Index
CDISC	Clinical Data Interchange Standards Consortium
CI	Confidence Interval
CR	Complete Response
CRF	Case Report Form
CRO	Contract Research Organization
CTCAE	Common Terminology Criteria for Adverse Events, version 5.0
ECG	Electrocardiogram
eCRF	Electronic Case Report Form
EE	Efficacy Evaluable
EOT	End of Treatment
FAS	Full Analysis Set
FPV	Fowlpox Virus
FU	Follow Up
ICF	Informed Consent Form
ICH	International Conference on Harmonisation (now International Council for Harmonisation)
IMAE	Immune Mediated Adverse Event
LTFU	Long Term Follow Up
MCHC	Mean Corpuscular Hemoglobin Concentration
MCV	Mean Erythrocyte Corpuscular Volume
MedDRA	Medical Dictionary for Regulatory Activities
MMR	Mismatch Repair
MSI	Microsatellite Instability
MVA-BN	Modified Vaccinia Ankara – Bavarian Nordic
NCI	National Cancer Institute
OR	Objective Response
ORR	Objective Response Rate
OS	Overall Survival
PD	Progressive Disease
PFS	Progression Free Survival
PR	Partial Response
PT	Preferred Term
RBC	Red Blood Cell/Erythrocyte
SAE	Serious Adverse Event
SAP	Statistical Analysis Plan
SC	Subcutaneous
SD	Stable Disease

Abbreviation	Definition
SD	Standard Deviation
SOC	System Organ Class
SOP	Standard Operating Procedure
TEAE	Treatment Emergent Adverse Event
TPS	Tumor Proportion Score
UC	Urothelial Cancer
WBC	White Blood Cell/Leukocyte
WHO DDE	World Health Organization Drug Dictionary Enhanced

General Definitions

Vaccination

A vaccination in this trial means receiving subcutaneous (SC) injection(s) with either MVA-BN-CV301 or FPV-CV301.

Trial Treatment

Trial treatment refers to dosing with any of the following trial products:

- Prime with MVA-BN-CV301 given SC on Days 1 and 22.
- Boost with FPV-CV301, given SC every 21 days for 4 doses, followed by boosts every 6 weeks until 6 months on trial, then every 12 weeks until completion of 2 years.
- Atezolizumab fixed dose of 1200 mg intravenous on Day 1 of each 21-day cycle.

Trial Medication

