- Related TEAEs, including the following subcategories:
 - TEAEs related to MVA-BN-CV301
 - TEAEs related to FPV-CV301
 - TEAEs related to atezolizumab
 - TEAEs related to trial product
- TEAEs \geq Grade 3
- Related TEAEs \geq Grade 3
- SAEs
- Related SAEs
- AESIs, including IMAEs and Cardiac Events
- Related AESIs
- TEAEs leading to discontinuation of treatment

In addition to the above summary categories, listings will also include the following:

- Baseline Signs and Symptoms
- TEAEs leading to death
- Post-treatment period SAEs and AESIs

A summary table of TEAEs will be created for the following categories: TEAEs, SAEs, AESIs, Related TEAEs, Severe TEAEs, Severe and Related TEAEs, Serious and Related TEAEs, TEAEs leading to discontinuation, and TEAEs leading to death. Event counts and subject incidences will be presented within each category and cohort, as well as overall, for the FAS.

The incidence for the above categories will be calculated as the number of subjects developing the specified AE type, divided by the number of subjects in the cohort. The incidence of AEs will also be calculated within each treatment period.

TEAEs will be summarized by SOC and PT and ordered by descending incidence of SOC, as well as descending incidence of PT within SOC. For TEAEs and related TEAEs, summaries will also be provided by

All AEs will be listed by subject, SOC, and PT. Per protocol, no new AEs should be reported during the LTFU phase, with the exception of related SAEs and related AESIs through 100 days post-last treatment. Any other AEs are reported during the LTFU phase will be listed and flagged as non-treatment emergent, but will not be included in the tables.

For summaries by relationship, CRF relationship categories will be dichotomized as related or unrelated per the above definition. Subjects experiencing more than one TEAE within an SOC or PT will be reported for the highest relationship category for the event of interest.

For summaries by severity, the CTCAE v5.0 grade will be used to summarize severe AEs including AEs \geq Grade 3. Again, if a subject has multiple AEs within an SOC or PT the most severe AE will be counted for the event of interest.

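### AE percentages by vaccine period set a planned 42-day MVA period beside an FPV period of up to 682 days, with no allowance for time at risk

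*SAP*

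**What the plan says.** SAP 4.3.4 assigns each AE to a period by its onset date. The MVA period takes "All AEs starting on the day of first MVA-BN-CV301 vaccination until the day prior to the first FPV-CV301" or, for those who stop sooner, up to early treatment termination. The FPV period takes "All AEs starting after the first FPV-CV301 vaccination through 30 days post-last trial product". An onset on a vaccination day follows that day's vaccine: "the AE will be assigned to the treatment period corresponding to the vaccination on this date to be conservative".

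SAP 4.4.8.1 then states: "Summary tables will be presented by treatment period (MVA Vaccination Period, FPV Vaccination Period, and Overall Treatment Period", with frequency and incidence given for TEAEs, related TEAEs by product, events of Grade 3 or higher, SAEs, AESIs and discontinuations. Incidence is the number of subjects with the event over the number of subjects in the cohort, and "The incidence of AEs will also be calculated within each treatment period". The SAP does not say whether the denominator changes by period.

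Neither document plans person-time, an exposure-adjusted rate, a per-dose rate or risk windows of equal length. Exposure (Protocol 9.9.3, SAP 4.4.7.10) is summarised as dose counts and total duration, plus dose interruptions in the protocol, but not as time at risk in each period. SAP 4.3.5 derives the onset day relative to the most recent vaccination, but no windowed incidence is built on it.

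**The concern.** The two periods differ greatly in planned length. The FPV period also varies by subject, because treatment normally stops at progression and may stop for toxicity (Protocol 4.2.5.1). Atezolizumab is given every 21 days in both. A crude percentage rises with time observed, so an event with a steady rate collects more subjects in the longer period. Event counts rise in the same way and do not correct this.

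Safety of the combination is a secondary objective and there is no control arm, so prime against boost is one of the few internal safety contrasts open to a reader. With the planned tables, a reader could not separate a true boost-phase increase from longer observation, and a true fall in rate could be hidden. Only descriptive safety tables are affected; the primary endpoint and its error rates are not.

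**Working it through.** The plan states no period length and no AE rate, so there is no figure of its own to reproduce.

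**Period lengths (inclusive days)**
- The SAP's General Definitions (Trial Treatment) give the prime doses: "Prime with MVA-BN-CV301 given SC on Days 1 and 22". The Protocol 1.4 synopsis gives the first boosts "on days 43, 64, 85, and 106". Since the MVA period runs "until the day prior to the first FPV-CV301", it covers Days 1-42, or 42 days.
- The last planned dosing day is Day 694 (Visit 14; Protocol 1.5 and 4.2.2.2). Adding 30 days gives Day 724. By the same-day rule the FPV period starts on Day 43, so its length is 724 - 43 + 1 = 682 days for a completer.
- The ratio of lengths is 682 / 42 = 16.2.

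**Constant daily rate, by day of last product**

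Assume 10% incidence in the MVA period. The hazard is -ln(0.9) / 42 = 0.002509 per day, and FPV incidence over d days is 1 - exp(-0.002509 × d).

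| Last product | FPV days at risk | FPV incidence | Ratio to 10% |
|---|---|---|---|
| Day 43 | 31 | 7.5% | 0.7 |
| Day 64 | 52 | 12.2% | 1.2 |
| Day 106 | 94 | 21.0% | 2.1 |
| Day 358 | 346 | 58.0% | 5.8 |
| Day 694 | 682 | 81.9% | 8.2 |

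The ratio cannot exceed 1 / (MVA incidence). For completers it is 11.3 at 5% and 2.0 at 50%.

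**With attrition**

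Assume exponential time on treatment, matched to the 16.8% progression-free at 12 months that Protocol 2.1 cites for second-line pembrolizumab. This is a proxy and not a forecast for this trial. The stopping rate is h = -ln(0.168) / 365.25 = 0.004884 per day (median about 4.7 months), with stopping day T capped at 694. MVA time is 42 days, or T if the subject stops before Day 43. FPV time is T + 30 - 42 = T - 12 for those who reach Day 43. The whole cohort is the denominator in both periods.

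- Share reaching FPV-CV301: exp(-0.004884 × 43) = 0.81.
- Mean FPV time per cohort subject: about 184 days.
- 10% event: MVA 9.1%, FPV 31.3%, ratio 3.5.
- 5% event: MVA 4.5%, FPV 18.3%, ratio 4.0.
- 50% event: MVA 45.7%, FPV 69.9%, ratio 1.5.
- Assumed median time on treatment of 2, 3 or 6 months instead: ratio 1.9, 2.5 or 4.0 for a 10% event.

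**What a person-time rate does**
- Constant daily rate: 0.002509 × 7 × 100 = 1.76 first events per 100 subject-weeks in both periods, so the distortion goes.
- Constant risk per dose: a completer has 2 primes in 42 days (one per 21) and 12 boosts in 682 days (one per 56.8). Equal risk per dose then gives a boost-period rate lower by a factor of 56.8 / 21 = 2.7, which is a distortion in the other direction.

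**The case against.** The case against has four parts.

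1. **No comparison is planned.** The objective concerns the combination, which the Overall Treatment Period table serves, and the by-period tables are descriptive. This stands, and it limits the importance of the point.
2. **Other summaries exist.** Relationship is collected for MVA-BN-CV301, FPV-CV301 and atezolizumab separately, with a table for each (SAP 4.4.8.1). These address the product question more directly. This stands in part: the tables are also crude and split by the same periods, and missing relationships count as related.
3. **The risk may follow doses.** Protocol 2.3.3 and 2.8.1 describe mainly local and flu-like reactions resolving within seven days of vaccination, and a prime dose is four injections against one for a boost. Such reactions need not follow a constant daily rate. This stands, and it is why a person-time column alone is not enough.
4. **Many subjects may stop early.** The first scan is at Day 64, and a subject stopping at or before then shows little or no inflation. If the whole cohort is the denominator, subjects who never reach FPV-CV301 lower the FPV percentage further. This stands; the attrition figures include both effects.

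A reader might go further and infer that the FPV columns are bound to show higher AE, SAE and AESI percentages, or that any excess there is mostly a matter of period length. The documents do not support either. They give no event rates by phase, the vaccine reactions they describe are tied to doses, and the result depends on how long subjects stay on treatment.

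**Conclusion.** The point holds as a limitation of descriptive tables. For events with a roughly constant daily rate, the planned percentages are inflated in the FPV period relative to the MVA period through period length, unless most subjects stop soon after Day 43. Under the attrition assumed above the inflation is about 3.5-fold for a 10% event, 4.0-fold for a 5% event and 1.5-fold for a 50% event. The 8-fold figure for a 10% event applies only to two-year completers and should not be read as typical.

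These sizes rest on three assumptions: the chosen MVA-period incidence, a constant rate across both periods, and a PFS proxy for time on treatment. The direction for constant-rate events and the lack of any time adjustment follow from the plan itself. The priority is low.

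**What to change.** In the by-period tables of SAP 4.4.8.1, keep the crude percentage and add:

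- **(a) A person-time rate.** Give subjects with a first event in the period per 100 subject-weeks at risk (period start to first event or period end), among subjects who entered that period. Show the number entering and the median and range of period length in the column header.
- **(b) A per-dose incidence for dose-related reactions.** Count events within a fixed window of equal length after each vaccination, divided by doses given, using the onset day already derived in SAP 4.3.5. Fix the window length and the list of reactions in the SAP before the analysis.

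Both use AE onset and dosing dates that are already collected, and trial conduct does not change. The costs are extra programming, wider tables, and rates that will be imprecise with 13 to 35 subjects per cohort. The rate in (a) assumes roughly constant risk within a period and would flatter the boost for per-dose reactions, so (b) should appear beside it.
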